3.3. Strata and Covariates

This study does not use a stratified randomization schedule when enrolling subjects. No covariates will be included in safety and efficacy analyses.

3.4. Subgroup Analyses

Subgroup analyses will be performed for the group of subjects who rolled over into the LTE due to failure to meet response/remission criteria at W10 (induction non-responders):

- Overall, and,
- By number of prior exposures to biologic agent (0 vs ≥ 1).

Subgroup analyses for efficacy endpoints are specified in Section 6.3.

3.5. Multiple Comparisons

Adjustments for multiplicity will not be made, because no formal statistical testing will be performed in this study.

3.6. Missing Data and Outliers

3.6.1. Missing Data

In general, missing data will not be imputed unless methods for handling missing data are specified. Exceptions are presented in this document.

For missing last dosing date of study drug, imputation rules are described in Section 4.2. Imputation and calculation rules for missing patient diary data are described in Section 6.1. The handling of missing or incomplete dates for AE onset is described in Section 7.1.6.2, and for concomitant medications in Section 7.4.

3.6.2. Outliers

Outliers will be identified during the data management and data analysis process, but no sensitivity analyses will be conducted. All data, including outliers, will be included in the data analysis, unless otherwise specified.

3.7. Data Handling Conventions and Transformations

In general, age (in years) on the date of the first dose of study drug will be used for analyses and presented in listings. If an enrolled subject was not dosed with any study drug, the enrollment date will be used instead of the first dosing date of study drug. If only the birth year is collected on the CRF, "01 July" will be used for the unknown birth day and month for the purpose of age calculation. If only birth year and month are collected, "15" will be used for the unknown birth day.

Non-pharmacokinetic data that are continuous in nature but are less than the lower limit of quantitation (LOQ) or above the upper LOQ will be imputed as follows:

- A value that is 1 unit less than the lower LOQ at the same precision level of the originally reported value will be used to calculate descriptive statistics if the datum is reported in the form of "< x" (where x is considered the lower LOQ). For example, if the values are reported as < 50 and < 5.0, values of 49 and 4.9, respectively, will be used to calculate summary statistics. An exception to this rule is any value reported as < 1 or < 0.1, etc. For values reported as < 1 or < 0.1, a value of 0.9 or 0.09, respectively, will be used to calculate summary statistics.
- A value that is 1 unit above the upper LOQ will be used to calculate descriptive statistics if the datum is reported in the form of "> x" (where x is considered the upper LOQ). Values with decimal points will follow the same logic as above.
- The lower or upper LOQ will be used to calculate descriptive statistics if the datum is reported in the form of "≤ x" or "≥ x" (where x is considered the lower or upper LOQ, respectively).

3.8. Analysis Visit Windows

3.8.1. Definition of Study Day

The First Dosing Date is defined as the date when subjects take the first dose of study drug in this study, as recorded in the Study Drug Administration eCRF.

The Last Dosing Date is defined as the date when subjects take the last dose of study drug in this study, as recorded in the Study Drug Administration eCRF.

Study day will be calculated from the first dosing date of study drug and derived as follows:

- For days on or after the first dosing date: Assessment Date – First Dosing Date + 1
- For days prior to the first dosing date: Assessment Date – First Dosing Date

Therefore, Study Day 1 is the day of first dose of study drug administration.

Baseline is defined as the last available observation on or prior to the first dosing date, unless otherwise specified.

3.8.2. Analysis Visit Windows

Subject visits might not occur on protocol-specified days. Therefore, for the purpose of analysis, observations will be assigned to analysis windows.

The analysis windows for CDAI, PRO2, vital signs, weight, hematology, and chemistry are provided in Table 3-1. The analysis windows for lipid profile, serum immunoglobulin, [REDACTED] [REDACTED] are provided in Table 3-2. The analysis windows for [REDACTED]

Table 3-1. Analysis Visit Windows for CDAI, PRO2, Vital Signs, Weight, Hematology and Chemistry

Nominal Visit	Nominal Study Day	Visit Window Study Day	
		Lower Limit	Upper Limit
Baseline	1	(none)	1
Week 2	15	2	22
Week 4	29	23	57
Week 12	85	58	127
Week 24	169	128	211
Week 36	253	212	295
Week 48	337	296	379
Week 60	421	380	463
Week 72	505	464	547
Week 84	589	548	631
Week 96	673	632	715
Week 108	757	716	799
Week 120	841	800	883

Nominal Visit	Nominal Study Day	Visit Window Study Day	
		Lower Limit	Upper Limit
Week 132	925	884	967
Week 144	1009	968	1051
Week 156	1093	1052	1135
Week 168	1177	1136	1219
Week 180	1261	1220	1303
Week 192	1345	1304	1387
Week 204	1429	1388	1471
Week 216	1513	1472	1555
Week 228	1597	1556	1639
Week 240	1681	1640	1723
Week 252	1765	1724	1807
Week 264	1849	1808	1891
Week 276	1933	1892	1975
Week 288	2017	1976	2059
Week 300	2101	2060	2143
Week 312	2185	2144	2227
Week 324	2269	2228	2311
Week 336	2353	2312	2395
Week 348	2437	2396	2479
Week 360	2521	2480	2563
Week 372	2605	2564	2647
Week 384	2689	2648	2731
Week 396	2773	2732	2815
Week 408	2857	2816	2899
Week 420	2941	2900	2983
Week 432	3025	2984	≥ 3025

CDAI = Crohn's Disease Activity Index; PRO2 = patient reported outcome consisting of 2 items: abdominal pain severity and liquid stool frequency

Table 3-2. Analysis Visit Windows for Lipid Profile, Serum Immunoglobulin,

Nominal Visit	Nominal Study Day	Visit Window Study Day	
		Lower Limit	Upper Limit
Baseline	1	(none)	1
Week 24	169	2	253
Week 48	337	254	421
Week 72	505	422	589
Week 96	673	590	757
Week 120	841	758	925
Week 144	1009	926	1093
Week 168	1177	1094	1261
Week 192	1345	1262	1429
Week 216	1513	1430	1597
Week 240	1681	1598	1765
Week 264	1849	1766	1933
Week 288	2017	1934	2101
Week 312	2185	2102	2269
Week 336	2353	2270	2437
Week 360	2521	2438	2605
Week 384	2689	2606	2773
Week 408	2857	2774	2941
Week 432	3025	2942	≥ 3025

3.8.3. Selection of Data in the Event of Multiple Records in an Analysis Visit Window

Depending on the statistical analysis method, single values may be required for each analysis window. For example, change from baseline by visit usually requires a single value, whereas a time-to-event analysis would not require 1 value per analysis window.

If multiple valid, nonmissing measurements exist in a postbaseline analysis window, records will be chosen based on the following rules if a single value is needed:

- The record closest to the nominal day for that visit will be selected.
- If there are 2 records that are equidistant from the nominal day, the later record will be selected.
- If there is more than 1 record on the selected day, the average will be taken for continuous data and the worse severity will be taken for categorical data, unless otherwise specified.

3.8.4. Definition of Baseline

Baseline in the LTE is defined as the last nonmissing value on or prior to the first dosing date of study drug in Study GS-US-419-3896, unless specified differently. If there are multiple records with the same time or no time recorded on the same day, the baseline value will be the average of the measurements for continuous data, or the measurement with the lowest severity (eg, normal will be selected over abnormal for safety electrocardiogram [ECG] findings) for categorical data.

4. SUBJECT DISPOSITION

4.1. Subject Enrollment and Disposition

Key study dates (ie, first subject enrolled, last subject enrolled, last subject last visit for the primary endpoint, and last subject last visit for the clinical study report) will be provided.

A summary of subject enrollment will be provided by treatment group for each country, investigator within a country, and overall. The summary will present the number and percentage of subjects enrolled. For each column, the denominator for the percentage calculation will be the total number of subjects analyzed for that column.

A summary of subject disposition will be provided by treatment group. This summary will present the number of subjects in each of the categories listed below:

- All Enrolled Analysis Set
 - By parent study (GS-US-419-4015, GS-US-419-4016, or GS-US-419-3895)
 - By reason for exiting parent study, i.e., either completed to end, due to failure to meet response/remission criteria at W10 or due to protocol-specified disease worsening)

- Safety Analysis Set

- Continuing study drug (for analysis other than the final analysis)
- Completed study drug
- Did not complete study drug with reasons for premature discontinuation of study drug
- Continuing study (for analysis other than the final analysis)
- Completed study
- Did not complete the study with reasons for premature discontinuation of study

For the status of study drug and study completion and reasons for premature discontinuation, the number and percentage of subjects in each category will be provided. The denominator for the percentage calculation will be the total number of subjects in the Safety Analysis Set corresponding to that column.

The following by-subject listings will be provided by subject ID number in ascending order to support the above summary tables:

- Reasons for premature study drug or study discontinuation

- Lot number and kit ID of assigned study medication

4.2. Extent of Study Drug Exposure and Adherence

Extent of exposure to study drug will be examined by assessing the total duration of exposure to study drug and the level of adherence relative to the study drug regimen specified in the protocol.

If subjects are continuing study drug at the data cutoff date for an interim analysis, the data cutoff date will be used to impute the last dosing date for the calculation of duration of exposure to study drug and adherence to the study drug.

4.2.1. Duration of Exposure to Study Drug

Total duration of exposure to study drug will be defined as last dosing date minus first dosing date plus 1, regardless of any temporary interruptions in study drug administration, and will be expressed in weeks using up to 1 decimal place (eg, 4.5 weeks). If the last study drug dosing date is missing (for subjects that have stopped treatment or the study as indicated by a study disposition record), the latest date among the treatment (study) disposition date, clinical visit date, laboratory sample collection date, and vital signs assessment date that occurred during the on-treatment period (i.e., after exposure start date) will be used for subjects included in the final analyses or the last available date in the database snapshot at the time of an interim analysis.

If month and year of the last dose are known, and the last study drug dosing date imputed above is different from the month collected, the last date of that month will be used. If only year of the last dose is known, and the last study drug dosing date imputed above is after the year collected, the last date of that year will be used; if the last study drug dosing date imputed above is before the year collected, the first date of that year will be used.

The total duration of exposure to study drug will be summarized using descriptive statistics and using the number (ie, cumulative counts) and percentage of subjects exposed through the following time periods: 1 day, 2 weeks, 4 weeks, 12 weeks, 24 weeks, 36 weeks, 48 weeks, 52 weeks, 60 weeks, and then every 12 weeks from Week 60. Summaries will be provided by treatment group for the Safety Analysis Set.

No formal statistical testing is planned.

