## **6.5. Post-Treatment Assessments ( $\pm$ 3 days)**

All subjects must complete the Post-Treatment (PTx) assessments 30 days after the last dose of study drug.

The following evaluations are to be completed:

- Symptom-directed PE
- Complete perianal fistulae assessment (for subjects rolling over from GS-US-419-4016 **only**)
- Obtain weight
- Review AEs and concomitant medications
- Obtain vital signs (resting blood pressure, respiratory rate, pulse and temperature)
- Obtain blood samples (reference Study Procedures Table [[Appendix 2](#)])
- Obtain urine sample (reference Study Procedures Table [[Appendix 2](#)])

— Sample will be used for pregnancy test (for females of childbearing potential only)

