4.2.2.1. On-Treatment Adherence

The level of on-treatment adherence to the study drug regimen will be determined by the total amount of study drug taken relative to the total amount of study drug expected to be taken during a subject's actual on-treatment period based on the study drug regimen.

The level of on-treatment adherence will be expressed as a percentage using the following formula:

$$\text{On - Treatment Adherence (\%)} = \left(\frac{\text{Total Amount of Study Drug Taken}}{\text{Study Drug Expected to be Taken on Treatment}} \right) \times 100$$

Descriptive statistics for the level of on-treatment adherence with the number and percentage of subjects belonging to adherence categories (eg, < 80%, ≥ 80 to < 90%, ≥ 90% to <120, ≥120) will be provided by treatment group for the Safety Analysis Set.

No formal statistical testing is planned.

A by-subject listing of study drug intake and drug accountability will be provided separately by subject ID number (in ascending order) and visit (in chronological order).

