7.1.6. Treatment-Emergent Adverse Events

7.1.6.1. Definition of Treatment-Emergent Adverse Events

Treatment-emergent adverse events (TEAEs) are defined as 1 or both of the following:

- Any AEs with an onset date on or after the study drug start date and no later than 30 days after permanent discontinuation of study drug
- Any AEs leading to premature discontinuation of study drug.

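### The missing last-dose rule in SAP 4.2.1 has no upper date limit, so read literally it can impute the post-treatment visit and add about 30 days of exposure

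*SAP*

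**What the plan says.** SAP 4.2.1 defines exposure this way: "Total duration of exposure to study drug will be defined as last dosing date minus first dosing date plus 1". If a subject has stopped and the last-dose date is missing, the SAP substitutes "the latest date among the treatment (study) disposition date, clinical visit date, laboratory sample collection date" or "vital signs assessment date that occurred during the on-treatment period (i.e., after exposure start date) will be used". For an interim analysis it allows the last date available in the snapshot, also without a stated upper end.

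A further paragraph handles partial dates. With month and year known, if "the last study drug dosing date imputed above is different from the month collected, the last date of that month will be used". With only the year known, the imputed date is pulled back inside that year.

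Protocol 6.5 states: "All subjects must complete the Post-Treatment (PTx) assessments 30 days after the last dose of study drug". The window is ± 3 days, and the visit includes vital signs and blood samples. Appendix 2 marks hematology and chemistry at PTx.

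Several other rules rest on the last-dose date:

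- SAP 3.6.1 refers missing last dosing dates to Section 4.2, without confining this to the exposure table.
- SAP 4.2.2.1 divides the amount taken by the "total amount of study drug expected to be taken during a subject's actual on-treatment period".
- SAP 7.1.6.1 ends the treatment-emergent window "no later than 30 days after permanent discontinuation of study drug". SAP 7.1.6.2 ties incomplete event dates to the last dose plus 30 days.
- SAP 7.2 and 7.2.2.1 end the laboratory window at the last dose plus 30 days.
- SAP 7.4 ends the concomitant-medication window at the last dosing date.

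**The concern.** The rule takes a maximum over dates, so its upper limit matters most, and that limit is absent. The phrase on-treatment period cannot supply it, because the date that would end the period is the one that is missing. The explanation in brackets gives only a start.

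Three of the four kinds of candidate date (visit, laboratory, vital signs) are recorded at PTx. The fourth can be the study disposition date rather than the treatment one, and that may be later still. The error in exposure therefore runs one way: too long. Safety is the primary endpoint, and exposure and the post-dose windows underlie its tables, so the imputed date should be close to the real last dose.

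**Working it through.** The plan gives no figure to reproduce here, and SAP 1.3 says no sample size calculation was done. The check is date arithmetic.

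**Inputs.** k = days from true last dose to PTx = 30, range 27 to 33 (Protocol 6.5). D = true exposure in days. The last-dose date is wholly missing and PTx was attended.

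**Exposure and adherence.** Imputed exposure is D + k. For a subject who took one daily dose throughout and whose tablet counts are complete, final-analysis adherence is D/(D + k). With k = 30:

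| D (days) | Imputed exposure | Increase | Adherence (true value 100%) |
|---|---|---|---|
| 84 | 114 | 30/84 = 35.7% | 84/114 = 73.7% |
| 336 | 366 | 30/336 = 8.9% | 336/366 = 91.8% |
| 672 | 702 | 30/672 = 4.5% | 672/702 = 95.7% |
| 2730 | 2760 | 30/2730 = 1.1% | 2730/2760 = 98.9% |

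At D = 84, k = 27 to 33 gives an increase of 32.1% to 39.3% and adherence of 75.7% to 71.8%.

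**Adherence categories.** D/(D + 30) is below 0.80 only when D < 0.8 × 30/0.2 = 120 days, and below 0.90 only when D < 0.9 × 30/0.1 = 270 days.

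**Month and year known.** I took each day of 2022 as the true last dose, set PTx at +30 days and applied the month-end rule. The mean overshoot is 14.7 days and the maximum 30. The maximum arises when the last dose is on the first of a 31-day month, because PTx then falls in the same month and nothing is corrected.

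**Year only known.** There is no correction when PTx falls in the same year.

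**Windows.** If permanent discontinuation is dated by the imputed last dose, the nominal adverse event cut-off moves from 30 days after the true last dose to k + 30 = 60 days (57 to 63). The laboratory limit moves likewise, so PTx samples from days 31 to 33, normally outside it, would enter. A drug started between the true last dose and PTx would be classed as concomitant.

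**Overall mean.** The share of subjects with a missing date is not given. Assuming 0.5% to 10%, mean exposure shifts by 30 × 0.005 = 0.15 to 30 × 0.10 = 3.0 days.

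**The case against.** The strongest reply is that the rule does say on-treatment and the protocol calls the visit post-treatment, so a sensible programmer would leave PTx out. That is a fair reading of intent. But the SAP explains the term in its own words, and those words admit any date after dosing began. The study disposition date is a candidate by name, which does not suggest a strict on-drug limit. Two programmers could obtain different dates.

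The reply is stronger on consequences:

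- **Adverse events.** A reader might infer that the off-drug event window doubles. Only the nominal cut-off does. Protocol 7.3.1 collects non-serious events until 30 days after the last administration, Appendix 2 runs collection through PTx, and Protocol 7.3.2 does not require sites to look for serious events afterwards. The data gain about 0 to 3 days plus occasional late serious reports. SAP 7.1.6.1 is also worded around permanent discontinuation, and the SAP does not say that an imputed date replaces a known discontinuation date.
- **Adherence.** A reader might infer that adherence is always lowered. SAP 4.2.2 counts an unreturned bottle as fully taken, which raises the numerator. At an interim, the count for an unreturned bottle moves with the last dosing date. The direction is then uncertain.
- **Lost subjects.** They normally have no PTx visit, so the 30-day figure does not describe them. A late study disposition date could, but the documents give no typical delay.
- **Event rates.** SAP 7.1.7.1 reports numbers and percentages of subjects, so longer exposure does not dilute a rate.

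Last dose is also an eCRF field (SAP 3.8.1), so wholly missing dates may be few.

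**Conclusion.** The point holds as a defect in a stated rule. As written, SAP 4.2.1 can impute the PTx visit or a later study disposition date as the last dose. For a stopped subject with a wholly missing date who attended PTx, exposure is too long by about 30 days (27 to 33). The relative error is large for short exposures and about 1% near the 7.5-year maximum. Known month and year reduce the average error to about 15 days; year alone may not reduce it. Adherence falls only where tablet counts are complete, and below 80% only when true exposure is under 120 days.

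The documents do not support a claim that safety conclusions are materially distorted: few extra adverse events are expected and the effect on overall means is probably small. These conclusions assume a literal reading of the rule and, for the windows, that the imputed date carries over from Section 4.2. The number of subjects affected is unknown.

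**What to change.** Amend SAP 4.2.1 as follows:

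1. End the on-treatment period at the treatment (study drug) discontinuation date or, if that is missing, at the early termination or end of treatment visit.
2. Impute the latest eligible date on or before that end. If neither end date exists, use the last visit, laboratory or vital-sign date before any PTx visit.
3. Exclude all PTx dates and the study, as opposed to treatment, disposition date.
4. Keep the month and year rules.
5. State that the same imputed date sets the adverse event, laboratory and concomitant-medication windows.

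I would not take the earliest candidate date or derive the last dose from tablet supply. Either could shorten true exposure and drop genuine on-drug events, and the supply method would make adherence partly circular.

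The cost is a few lines of text and programming, with slightly shorter exposure for a few subjects. Some error remains where the early termination visit itself falls after the last dose. SAP section 1 already allows changes after finalization to be documented in the study report.

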4.2.2. Adherence to Study Drug

The total number of tablets taken will be summarized using descriptive statistics.

The presumed total number of tablets taken by a subject will be determined by the data collected on the drug accountability CRF using the following formula:

$$\text{Total Number of Tablets Taken} = \left(\sum \text{No. of Tablets Dispensed} \right) - \left(\sum \text{No. of Tablets Returned} \right)$$

If the bottle was not returned, it is assumed that the subject took all the study drug tablets from the dispensed bottle. The number of tablets returned will be imputed as zero for the given bottle for study drug adherence calculation purposes.

For calculation of the total number of tablets taken for the purposes of interim analyses (ie, prior to the return of all drug bottles), it will be assumed that each subject took the recommended daily dose from the dispensed bottle(s) until either the date of discontinuation, death or data cutoff date (whichever is earliest).

If the bottle has not been returned yet when the interim analysis is conducted, the number of tablets returned will be imputed as total pill count in the dispensed bottle – (the last dosing date – the last bottle dispensed date +1) for the given bottle for study drug adherence calculation purposes.

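### In the final analysis, an unreturned bottle counts as fully taken with no limit at the last dosing date, which overstates adherence for subjects who stop mid-supply

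*SAP*

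**What the plan says.** SAP 4.2.2 takes the presumed number of tablets taken as the sum dispensed minus the sum returned. For a missing bottle the default rule is "If the bottle was not returned, it is assumed that the subject took all the study drug tablets from the dispensed bottle", implemented as "The number of tablets returned will be imputed as zero for the given bottle for study drug adherence calculation purposes". This rule is not tied to any date.

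Two further paragraphs of SAP 4.2.2 apply to interim analyses only. One assumes the recommended daily dose up to discontinuation, death or data cutoff, whichever comes first. The other covers a bottle not yet back: "the number of tablets returned will be imputed as total pill count in the dispensed bottle" less the days from the last dispensing to the last dosing date, counted inclusively.

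SAP 4.2.2.1 divides the amount taken by the amount expected during the subject's "actual on-treatment period based on the study drug regimen". Results are grouped as below 80%, 80% to below 90%, 90% to below 120%, and 120% or more.

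SAP 4.2.1 defines duration of exposure as first to last dose, "regardless of any temporary interruptions in study drug administration". It imputes a missing last dosing date, for the final analysis, from the latest of several disposition, visit, laboratory and vital signs dates.

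**The concern.** Numerator and denominator cover different time spans. The denominator ends with treatment. The numerator, for an unreturned bottle in the final analysis, runs to the bottom of the bottle whenever treatment ended. The same bottle would be limited by the last dosing date at an interim analysis, so the final analysis is the less accurate of the two although more is known by then.

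Protocol 5.6 requires all used and unused drug to be returned, so a missing bottle is an exception. It is plausibly more common among subjects who leave without a closing visit, although the documents give no rate. At stake is the adherence table: some early leavers would appear to have taken far more drug than they could have, and some poor takers would be lifted into an acceptable category.

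**Working it through.** The documents state no adherence figure to reproduce, so the check applies the SAP's own formulas to worked cases.

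**Inputs from the documents**
- Bottle size: 30 tablets (protocol 5.2.2).
- Dosing: once daily (protocol 5.3).
- Dispensing: Day 1, Week 4, Week 12, then every 12 weeks (protocol Appendix 2).

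**Assumptions, not in the documents**
- Three bottles, 90 tablets, per 84-day supply.
- One tablet a day. A two-tablet blinded regimen with both bottle types unreturned doubles numerator and denominator and gives the same ratio.
- All earlier bottles returned, and only the last supply missing.
- Full intake up to the stop, unless stated otherwise.

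**1. Last dosing date recorded.** Let S be the days before the last dispensing and a the days from dispensing to last dose, inclusive. The final rule gives adherence = (S + 90)/(S + a). A cap at the last dose gives (S + a)/(S + a) = 100%, the true value. With a = 14:

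| Last dispensing | S | Final rule | Capped |
|---|---|---|---|
| Week 12 | 84 | 174/98 = 177.6% | 100% |
| Week 24 | 168 | 258/182 = 141.8% | 100% |
| Week 48 | 336 | 426/350 = 121.7% | 100% |
| Week 96 | 672 | 762/686 = 111.1% | 100% |
| Week 240 | 1680 | 1770/1694 = 104.5% | 100% |

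For stops from 1 to 70 days into the supply, the result ranges from 174/85 = 204.7% down to 174/154 = 113.0% at Week 12, and from 1770/1681 = 105.3% down to 1770/1750 = 101.1% at Week 240.

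With a = 14 the result reaches 120% only while S + 90 ≥ 1.2(S + 14), that is S ≤ 73.2/0.2 = 366 days.

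**2. A subject who was not adherent.** Take a subject with 75% intake throughout who stops 14 days into the Week 24 supply.
- True: 0.75 × 182 = 136.5 tablets, 75%, in the lowest category.
- Final rule: (126 + 90)/182 = 118.7%, in the 90% to below 120% category.
- Capped: (126 + 14)/182 = 76.9%, back in the lowest category.

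**3. Last dosing date missing.** If SAP 4.2.1 imputes a date g days after the true stop, the Week 12 case becomes 174/(98 + g):
- g = 30: 174/128 = 135.9%
- g = 76: 174/174 = 100.0%
- g = 120: 174/218 = 79.8%

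The numerator is still inflated, but the percentage need not be.

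**4. Why the cap must be allocated once.** The interim formula is written per bottle. Applied to three bottles dispensed together with 14 days of treatment, it imputes 30 − 14 = 16 returned from each and credits 3 × 14 = 42 tablets for 14 days. At 40 days it imputes 30 − 40 = −10 returned per bottle. Copying it unchanged into the final rule would not be enough.

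**The case against.** **The consequence is small.** Adherence is descriptive and no endpoint, analysis set or test depends on it. Exposure duration is computed from dates, so the tablet rule does not affect it. SAP 4.2.2 calls the count presumed and states its assumption openly. The category of 120% or more would show the largest errors, and a by-subject accountability listing is planned. With treatment of up to about 7.5 years (protocol 3.4), the distortion for long-term subjects is a few percent. All of this stands and limits the weight of the point. The category is only a partial safeguard, as the 118.7% case shows.

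**Overstatement is not assured for everyone who is lost to follow-up.** A reader might infer that it is. These are the subjects most likely to lack a recorded last dose, and the SAP 4.2.1 imputation can then enlarge the denominator. The claim of overstatement is therefore limited to subjects with a recorded date.

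**Protocol-directed interruptions.** A reader might infer that they are scored as missed doses, so that a subject who followed protocol 3.5.1 appears non-adherent. The documents do not say this. The phrase "regardless of any temporary interruptions in study drug administration" belongs to exposure duration, and nothing makes that duration the adherence denominator. SAP 4.2.2.1 leaves the on-treatment period undefined, and excluding interruption days is an equally open reading. The choice matters for short follow-up. With otherwise full intake, a 28-day interruption scores (168 − 28)/168 = 83.3% over 24 weeks, 308/336 = 91.7% over 48 weeks and 1652/1680 = 98.3% over 240 weeks if the days are kept, and 100% if they are excluded. That supports a request for clarification, not a finding of error.

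**Conclusion.** The point holds for unreturned bottles in the final analysis when the last dosing date is recorded. Followed as written, the rule credits tablets after the last dose. It turns true adherence of 100% into 178%, 142%, 122% and 104% for a stop 14 days into the Week 12, 24, 48 and 240 supplies. These figures rest on 90 tablets per 12-week supply, full intake before the stop and only the last supply unreturned. The number of subjects affected cannot be derived from the documents.

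Where the last dosing date is imputed, the direction is uncertain. The handling of interruption days is unspecified rather than wrong. It would go too far to say that the exposure results are affected. This is a minor point, limited to the adherence summary.

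**What to change.** In SAP 4.2.2, for unreturned bottles in the final analysis, credit no more than the regimen's daily tablets multiplied by the days from dispensing to the last dosing date, inclusive. Allocate those days once across bottles dispensed together, and never credit more than the tablets dispensed. Report the number of subjects with any unreturned bottle by treatment group, so that readers can see how far the summary rests on imputation.

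As a clarification only, state in SAP 4.2.2.1 whether recorded interruption days are excluded from the expected amount.

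The cost is a few sentences and minor programming. The dispensing and last dosing dates are already used in the interim rule, so that part needs no new data.
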